2.8.4 Other safety data

2.8.4.1 ECG and cardiac imaging data

Not applicable.

2.8.4.2 Vital signs

Sample statistics of vital signs were presented for V2/BL/M0 as well as the last value until V7/M36 and the change (i.e. difference) between these time points. The average of the three measurements of blood pressure was analysed.

[figure not shown]
Abnormal values for pulse, diastolic and systolic blood pressure was defined in the study protocol. A shift table for abnormal values at baseline versus post-baseline was presented. For the post-baseline period, an abnormality was counted if it occurred at any visit after V2/BL/M0.

2.9 Pharmacokinetic endpoints

No pharmacokinetic endpoints were defined.

2.10 PD and PK/PD analyses

No pharmacodynamics/pharmacokinetic endpoints were defined.

2.11 Biomarkers

2.13 Not applicable. Other Exploratory analyses

Not applicable.

2.14 Interim analysis

Not applicable.

3 Sample size calculation

Published data varies widely as to the average thinning of RNFL in MS patients and no data is available on patients treated with Fingolimod. As this is an explorative study to get a better understanding of RNFL thinning in RRMS treated with Fingolimod we will take a representative sample of approximately 100 patients with RRMS who are stable on Fingolimod

4 Change to protocol specified analyses

[figure not shown]
The change in ganglion cell layer thickness (GCLT) was defined as secondary endpoint, but OCT measured the ganglion cell inner plexiform layer (GCIP). This was done because both layers are not clearly separable by OCT. The volume of GCIP is declared as usual parameter.

5 Appendix

5.1 Imputation rules

Missing dates are completed by 15th for missing days and 6th for missing months.

Imputation of primary and secondary parameters are described above.

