5.1 Inclusion/exclusion criteria

Inclusion Criteria

Patients eligible for inclusion in this study have to fulfill all of the following criteria:

1. Written informed consent must be obtained before any assessment is performed.
2. Male or female subjects aged 18-65 years.
3. Subjects with relapsing remitting MS defined by 2010 revised McDonald criteria (see [Appendix 4](#)).
4. Patients with Expanded Disability Status Scale (EDSS) score of 0-6.0 inclusive (see [Appendix 6](#)).
5. Patients stable on immunomodulatory treatment with fingolimod for at least 28 days and at most 4 months prior to screening according to local label
6. Neurologically stable with no evidence of relapse within 30 days prior to inclusion date (visit 2)
7. Sufficient ability to read, write, communicate and understand

Exclusion Criteria

Patients fulfilling any of the following criteria are not eligible for inclusion in this study:

1. Patients who have been treated with:

- systemic corticosteroids or immunoglobulins within 1 month prior to screening;
 - immunosuppressive medications such as azathioprine, cyclophosphamide, or methotrexate within 3 months prior to screening;
 - monoclonal antibodies (including natalizumab) within 3 months prior to screening;
 - mitoxantrone within 6 months prior to screening
 - cladribine at any time.
2. Patients with any medically unstable condition, as assessed by the primary treating physician at each site.
 3. Patients with any of the following cardiovascular conditions :
 - history of myocardial infarction or with current unstable ischemic heart disease;
 - Heart failure (NYHA III-IV) or any severe cardiac disease as determined by the Investigator (see [Appendix 5](#));
 - history or presence of a second-degree AV block, Type II or a third-degree AV block
 - patients receiving Class Ia (ajmaline, disopyramide, procainamide, quinidine) or III antiarrhythmic drugs (e.g., amiodarone, bretylium, sotalol, ibutilide, azimilide, dofetilide);
 - proven history of sick sinus syndrome;
 - uncontrolled hypertension
 4. Patients with severe respiratory disease, pulmonary fibrosis, or chronic obstructive pulmonary disease (Class III-IV).
 5. Patients with history of specific MRI findings (tumor, subdural haematoma, post-contusional changes, territorial stroke, neurodegenerative disorders, aneurysm/arteriovenous malformation, evidence of past macroscopic haemorrhage, or other relevant MRI findings that would interfere with evaluation)

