8.1 Adverse Events (AEs)/Serious Adverse Events (SAEs)

An adverse event is the appearance or worsening of any undesirable sign, symptom, or medical condition occurring after first drug intake even if the event is not considered to be related to drug therapy. Medical conditions/diseases present before obtaining informed consent are only considered adverse events if they worsen after starting trial. Abnormal laboratory values or test results constitute adverse events only if they induce clinical signs or symptoms, are considered clinically significant, require medication discontinuation or require therapy.

The occurrence of adverse events should be sought by non-directive questioning of the patient at each visit during the trial. Adverse events also may be detected when they are volunteered by the patient during or between visits or through physical examination, laboratory test, or

other assessments. All adverse events must be recorded on the Adverse Events CRF with the following information:

1. its relationship to Fingolimod (suspected/not suspected)
2. its duration (start and end dates or if continuing at final exam)
3. whether it constitutes a serious adverse event (SAE)

An SAE is defined as an event which:

- is fatal or life-threatening
- results in persistent or significant disability/incapacity
- constitutes a congenital anomaly/birth defect
- requires inpatient hospitalization or prolongation of existing hospitalization, unless hospitalization is for:
 - routine treatment or monitoring of the studied indication, not associated with any deterioration in condition (e.g. hospitalization for relapse treatment)
 - elective or pre-planned treatment for a pre-existing condition that is unrelated to the indication under study and has not worsened since the start of study drug
 - treatment on an emergency outpatient basis for an event not fulfilling any of the definitions of a SAE given above and not resulting in hospital admission
 - social reasons and respite care in the absence of any deterioration in the patient's general condition
- is medically significant, i.e., defined as an event that jeopardizes the patient or may require medical or surgical intervention to prevent one of the outcomes listed above

Unlike routine safety assessments, SAEs are monitored continuously and have special reporting requirements; see Section 8.2.

Information about adverse reactions observed in relation to fingolimod can be found in the local product labeling.

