9.3 Database management and quality control

Data from the CRFs are entered into the study database by Contract Research Organization staff following their own internal standard operating procedures that have been reviewed and approved by Novartis.

Subsequently, the entered data are systematically checked by Data Management staff, using error messages printed from validation programs and database listings. Obvious errors are corrected by Data Management personnel preliminarily. However, a listing with these performed obvious corrections will be sent to the respective investigators for approval. Other errors or omissions are entered on Data Query Forms, which are returned to the investigational site for resolution. The signed original and resolved Data Query Forms are kept with the CRFs at the investigator site, and a copy is sent to Novartis so the resolutions can be entered into the database. Quality control audits of all key safety and efficacy data in the database are made prior to locking the database.

Concomitant medications entered into the database will be coded using the WHO Drug Reference List, which employs the Anatomical Therapeutic Chemical classification system. Medical history/current medical conditions and adverse events will be coded using the Medical dictionary for regulatory activities (MedDRA) terminology.

OCT assessments (including last OCT measurement prior to first intake of fingolimod, if available) are evaluated and quality controlled centrally by Dr. [REDACTED], data will be recorded and stored at [REDACTED].

Laboratory samples will be processed locally.

At the conclusion of the study, the occurrence of any protocol violations will be determined. After these actions have been completed and the database has been declared to be complete and accurate, it will be locked and made available for data analysis. Any changes to the database after that time can only be made by joint written agreement between the Trial Statistician and Statistical Reporting and the Clinical Trial Leader.

10 Data analysis

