1.1 Study design

This is a multi-center, open-label study in RRMS patients treated with fingolimod. After signing the informed consent, patients will enter a Screening Phase (day -28 to day 0) before starting the study at Baseline (visit 2/day 0), followed by a 36-month longitudinal data collection phase. Visits are performed at month 3 (visit 3), month 6 (visit 4), month 12 (visit 5), month 24 (visit 6), and month 36 (visit 7). Eligibility will be determined at Screening. OCT and other assessments will be performed according to the schedule in Table 7-1 of the Clinical Study Protocol (CSP).

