Secondary	To evaluate safety and tolerability of fingolimod in MS patients followed for up to 36 months and specifically to determine the frequency of macular edema under treatment with oral fingolimod in this patient population	
Incidence of adverse events, serious adverse events and (S)AEs at least possible related to fingolimod in the Safety Set (SAF)
 
Incidence of macular edema (AE of special interest)

Last value until Visit x The last (post-baseline) value documented until Visit x, i.e. missing or invalid data are replaced by the last available value. Baseline values are not carried forward.

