2.8.1 Adverse events (AEs)

Adverse events which started before BL/M0 were listed only. Analyses were performed on AEs which started at/after BL/M0.

The incidence of adverse events is displayed with n, percentage and 95% confidence interval for the SAF. Here, different types of AEs are presented:

- (1) Any AE
- (2) AE with suspected relationship to fingolimod
- (3) AE leading to study drug dosage adjustment/temporary interruption
- (4) AE leading to permanent study drug discontinuation
- (5) Serious adverse event
- (6) Non-Serious AE
- (7) Death

For AEs of type (1) to (6) a two-level frequency table for MedDRA system organ classes (SOC) and Preferred Terms (PT) within SOC are presented. Here, a patient with multiple occurrences is counted only once on the respective class.

The maximum severity of (several) AEs occurring in a patient ist displayed for PTs within SOC, SOC and overall.

For AEs of type (7), (5), and (3) separate listings are generated.

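### If SAP 5.1's fixed 15th/June completion is used for AE onset, an onset can fall after the AE's own end date, and an AE that ended before baseline can be tabulated (very small effect)

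*SAP*

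**What the plan says.** SAP 5.1 (Imputation rules) states: "Missing dates are completed by 15th for missing days and 6th for missing months". The only other sentence there refers the primary and secondary parameters to earlier sections. The rule names no variable and makes no reference to baseline or to an end date.

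SAP 2.8.1 makes the onset date decisive: "Adverse events which started before BL/M0 were listed only. Analyses were performed on AEs which started at/after BL/M0". What is analysed there supports a secondary endpoint in SAP 1.2: "Incidence of adverse events, serious adverse events and (S)AEs at least possible related to fingolimod in the Safety Set (SAF").

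Protocol 8.1 requires for every AE "its duration (start and end dates or if continuing at final exam"), so the end date needed to check an imputed onset is already collected.

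No AE-specific rule for partial dates appears in the text available to us. That text lacks SAP 5.2 and most of SAP 2.1.

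**The concern.** A fixed mid-month or mid-year date ignores what is known about the same event. If the end date is on record, the onset cannot be later, yet the rule allows it. Near baseline this matters, because the imputed onset decides whether the AE is tabulated or only listed. An AE that was demonstrably over before baseline can then count in the incidence tables.

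Such AEs can exist in the database. There is a "Screening Phase (day -28 to day 0") before baseline. Protocol 8.1 defines an AE as a "medical condition occurring after first drug intake even if the event is not considered to be related to drug therapy", and patients must already have been on "fingolimod for at least 28 days and at most 4 months prior to screening". SAP 2.8.1 itself provides a listing for AEs that started before baseline.

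At stake is the internal consistency of the AE data and, marginally, the AE counts. The primary endpoint is not involved.

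**Working it through.** The plan states no figure on this point, so there is none to reproduce.

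**Inputs from the documents**
- Missing day becomes 15; missing month becomes June (SAP 5.1).
- Tabulated if onset is on or after baseline (SAP 2.8.1).
- Pre-baseline window of 28 days and follow-up of 36 months (SAP 1.1), taken as 1,096 days including day 0.

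**Assumptions not in the documents**
- Baseline dates are spread evenly over 365 days, and AE onset is uniform at the same rate before and after baseline.
- 2-20% of AEs lack the day; 0.5-5% lack day and month. The low rates are taken together, and the high rates together.

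**Step 1: the example.** Baseline 10 March, end 8 March, onset in March with day unknown. Imputed onset is 15 March. It is after the end (15 > 8) and not before baseline (15 ≥ 10), so the AE is tabulated although it ended before baseline.

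**Step 2: onset after a known end.** Let the AE end L days after onset, with onset equally likely on any day of the year.
- Day missing: onset must be before day 15 − L of its month, giving 12 × (14 − L) of 365 days. L = 1: 156/365 = 43%. L = 3: 132/365 = 36%. L = 7: 84/365 = 23%. L ≥ 14: 0%.
- Day and month missing: 15 June is day 166, giving (165 − L)/365. L = 1: 164/365 = 45%. L = 30: 135/365 = 37%.

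These are shares of AEs with a partial onset and a known end in the month or year concerned, not shares of all AEs.

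**Step 3: wrong entries into the tables.** Count pairs of baseline date and onset 1-28 days earlier whose imputed onset is on or after baseline.
- Day missing: baseline on day b ≤ 15 gives b − 1 pairs. The sum for b = 1 to 15 is 105 per month, × 12 = 1,260.
- Day and month missing: baseline on day B ≤ 166 of the year gives min(B − 1, 28) pairs, so 378 + 138 × 28 = 4,242.
- Denominator, post-baseline onsets: 365 × 1,096 = 400,040.
- Low rates: (0.02 × 1,260 + 0.005 × 4,242)/400,040 = 46.4/400,040 = 0.012%.
- High rates: (0.20 × 1,260 + 0.05 × 4,242)/400,040 = 464.1/400,040 = 0.116%.

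**Step 4: what an end-date bound does.** If the end is before baseline, the AE is correctly moved to the listing. If the end is on or after baseline, the earlier of the 15th and the end date is on or after baseline exactly when the 15th is, so the classification does not change. The bound can therefore only remove errors. If all end dates are known and durations are exponential with mean m days (assumed), an onset k days before baseline remains an error with weight exp(−k/m):

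| m | day-missing count | month-missing count | low rates | high rates |
|---|---|---|---|---|
| 3 | 348.7 | 410.7 | 0.002% | 0.023% |
| 30 | 1,061.4 | 2,750.4 | 0.009% | 0.087% |

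**Step 5: the opposite error.** The rule can also move a true post-baseline onset to the listing: baseline 20 March, onset 25 March with day unknown, imputed 15 March. The counts are 1,523 (day missing) and 19,900 (month missing), giving (0.02 × 1,523 + 0.005 × 19,900)/400,040 = 0.032% at the low rates and 0.325% at the high rates. No recorded end date contradicts these, and the end-date bound leaves them unchanged.

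**The case against.** The strongest objection is that the premise is unproven. SAP 5.1 does not name AE dates, and an AE rule may stand in SAP 5.2 or in the part of 2.1 that we do not have. This stands, which is why the point is conditional and why naming the governing rule would close it.

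Second, the documents provide a prior control. Protocol 9.3 says: "Other errors or omissions are entered on Data Query Forms, which are returned to the investigational site for resolution". Some partial dates would be resolved before any imputation, and the documents give no rate for those that remain. This also stands; the percentages rest on assumed rates. But a completion rule is in the SAP because some missing dates are expected to remain.

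Third, no decision turns on it. The study is single-arm, SAP 2.5.2 and 2.7.2 test no hypothesis, and patients take fingolimod on both sides of baseline. An error moves an AE between table and listing, not between untreated and treated time. This stands in full and limits the point to a minor one.

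A reader might also infer more than the documents support:
- **A window running back to first drug intake**, with more pre-baseline AEs at risk. Protocol 8.1 goes on to say that conditions present before consent count as AEs only if they worsen after the trial starts. The 28-day screening window is the better supported one, and it is itself the maximum.
- **Defaulting every undecidable onset to post-baseline.** Without end dates this replaces error counts of 2,783 (day: 1,260 + 1,523) and 24,142 (month: 4,242 + 19,900) by 5,348 and 9,814. With 20% of days and 0.5% of months missing, total error rises from (0.20 × 2,783 + 0.005 × 24,142)/400,040 = 0.169% to (0.20 × 5,348 + 0.005 × 9,814)/400,040 = 0.280%. It is a trade-off, not a correction.

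**Conclusion.** The point holds in conditional form and is minor. Read plainly, SAP 5.1 can produce an AE onset later than the recorded end, and through SAP 2.8.1 it can tabulate an AE that ended before baseline. One record with the right dates is enough to show this; no assumed rate is needed.

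The size is very small: about 0.01-0.12% of post-baseline AEs entered wrongly, or 0.1 to 1.2 per 1,000, under the assumed missing rates and even spread of dates. Not all of these have an end date before baseline, so the part that the bound removes is smaller still. Incidence counts a patient once per class, which should dilute the effect further at patient level; that was not computed.

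Partial dates away from baseline are unaffected only as regards the baseline split. An onset after the end date can arise in any month, but there it changes no planned output, because SAP 2.8.1 contains no analysis of AE duration or time to onset.

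The documents do not support a claim that AE incidence is materially biased, or that the plan certainly misclassifies AEs.

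**What to change.** Add to SAP 5.1, for AE onset:
1. An imputed onset is never later than a known end date.
2. An AE with a known end date before baseline is classified as pre-baseline.
3. Imputed onsets are flagged in the AE listings.

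Otherwise keep the 15th/June. If 5.1 is not meant for AE dates, say so and name the rule that is.

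The cost is two or three sentences and a few lines of code, using dates that the protocol already collects. There is no statistical cost, since the bound can only remove errors (step 4). It does nothing for AEs without a known end date or for the opposite error in step 5. The flag lets a reader see how many AEs are involved.

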5.3 Statistical models

5.3.1 Primary analysis

See 2.5 Analysis of the primary objective.

5.3.2 Key secondary analysis

The SAS syntax for mixed model to compare RNFLT in eyes with versus without optic neuritis is:

```
proc mixed data=test5;
```

```
class patno opt_neur ;
model rnflt = opt_neur;
random patno;
lsmeans krank / tdiff pdiff;
run;
```

RNTFL ist the difference from BL to last value until M36. Here no average over both eyes is calculated, but each measurement is included in the dataset and flagged in OPT_NEUR if the respective eye was affected by optic neuritis history.

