6.6.3 Recommendations on treatment of MS relapse

Following an onset of MS relapse the patient may have unscheduled visits in the investigator's discretion. Handling of MS relapses will be performed according to local practice and standard of care procedures.

A standard course of corticosteroids (methylprednisolone) on an inpatient or outpatient basis is allowed for treatment of relapses as clinically warranted and should be recorded in the CRF.

Steroid treatment should consist of 3-5 days and up to 1,000 mg methylprednisolone/day. Standard of care procedures will be followed during treatment.

Use of any oral tapering is not permitted.

The use of steroid for MS relapses therapy should be recorded on the "Prior-/concomitant medications" CRF.

Investigators should consider the added immunosuppressive effects of corticosteroid therapy and increase vigilance regarding infections during such treatment and in the weeks following administration.

Should a patient show evidence or suspicion of infection, please refer to actual Summary of product Characteristics.

In the event that steroids are administered patients should be reminded of the importance of reporting any signs or symptoms of an infection. Special consideration should be given to symptoms or signs of herpes simplex or zoster reactivation (e.g. lancinating pain, skin lesions) and appropriate antiviral therapy (e.g. acyclovir, valacyclovir) should be promptly initiated

and continued for up to 30 days after stopping high dose steroid treatment. An infectious disease specialist may be consulted to guide such therapy if needed.

Should a patient develop any neurological symptoms or signs, unexpected for MS in the opinion of the investigator or accelerated neurological deterioration, the investigator should immediately schedule an MRI according to local practice.

In case of acute optic neuritis or MS relapse the OCT assessment should be postponed for at least 30 days (at the discretion of the investigator) and the circumstance must be recorded in the corresponding CRF.

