10.5 Analysis of secondary [REDACTED] objectives

10.5.1 Secondary [REDACTED] outcomes

Secondary endpoints like changes in quadrant RNFLT, changes in total macular volume (TMV), and changes in ganglion cell layer thickness (GCLT) from baseline to months 12, 24, and 36 will be evaluated with a paired t-test or Wilcoxon signed-rank test, as appropriate.

Changes in OCT parameters between eyes with and without history of optic neuritis will be evaluated with a paired t-test or Wilcoxon signed-rank test, as appropriate.

[REDACTED]

Additionally, means, standard deviations, median, minimum and maximum will be presented for each visit, as will be the change from baseline. These descriptive statistics will also be presented for the primary endpoint.

For all other [REDACTED] endpoints summary statistics will be presented. Summary statistics will include n (number of observations), mean, standard deviation, median, minimum and maximum values at each visit, as well as the change.

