1.2 Study objectives and endpoints

The primary objective is to evaluate the change in average RNFL thickness (RNFLT) in RRMS patients treated with fingolimod over 36 months as assessed by OCT. The average RNFL thickness following OCT assessment will be calculated for the left and right eye per visit and per patient. The following table describe the objectives and endpoints:

	Objective	Endpoint
Primary	To evaluate the change in average RNFL thickness (RNFLT) in RRMS patients treated with fingolimod over 36 months as assessed by OCT	Absolute Difference in mean RNFLT from baseline (BL) to M36 (or last values in case of missing data) in the full analysis set (FAS). Mean RNFLT is the average of valid measurements of right and left eye. Sensitivity analyses are performed with the Per-Protocol Set (PPS) and for relative change (M36/BL)
Secondary	To compare changes in OCT parameters between eyes with and without history of optic neuritis	Absolute Difference in RNFLT from baseline (BL) to M36 (or last values in case of missing data) in the full analysis set (FAS) for: - eyes with versus without optic neuritis
Secondary	To evaluate the change in average RNFLT under fingolimod therapy from	Absolute Difference and ratios in average RNFLT from baseline (BL) to M12 respectively M24 (or last values in case of missing data) in the full analysis set (FAS).

	Objective	Endpoint
	baseline to months 12 and 24 as assessed by OCT	
Secondary	To evaluate change in quadrant RNFLT under fingolimod therapy from baseline to months 12, 24 and 36	
Absolute Difference and ratios in average quadrant RNFLT from baseline (BL) to M12, resp. M24 resp. M36 (or last values in case of missing data) in the full analysis set (FAS).
 
Quadrant RNFLT are:
 
 - Nasal-inferior - Nasal-superior - Temporal.inferior - Temporal-superior
Secondary	To evaluate changes in total macular volume (TMV) under fingolimod therapy from baseline to months 12, 24 and 36	Absolute Difference and ratios in average TMV from baseline (BL) to M12, resp. M24 resp. M36 (or last values in case of missing data) in the full analysis set (FAS).
Secondary	To evaluate changes in ganglion cell layer thickness (GCLT) under fingolimod therapy from baseline to months 12, 24 and 36	Absolute Difference and ratios in average GCLT from baseline (BL) to M12, resp. M24 resp. M36 (or last values in case of missing data) in the full analysis set (FAS).

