2.5.4 Supportive analyses

A comparison for eyes with versus without optic neuritis is done by a mixed model including the subject as random factor. LSMMeans for RNFLT in eyes with versus without optic neuritis are displayed as well as the difference including p-value.

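### Does the wrong variable name in the optic-neuritis code, or the undated history flag, call for a change to the SAP?

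*SAP*

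**What the plan says.** The secondary objective in SAP 1.2 is "To compare changes in OCT parameters between eyes with and without history of optic neuritis". The endpoint cell beside it shortens the grouping to "eyes with versus without optic neuritis".

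SAP 2.5.4 specifies a mixed model with subject as a random factor and names the output: "LSMMeans for RNFLT in eyes with versus without optic neuritis are displayed as well as the difference including p-value".

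SAP 5.3.2 prints the code. The LS-means line is "lsmeans krank / tdiff pdiff". The note below it gives the outcome, "RNTFL ist the difference from BL to last value until M36", and says that each eye enters separately, "flagged in OPT_NEUR if the respective eye was affected by optic neuritis history".

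The protocol bears on this in two places. Section 10.5.1 says that changes in OCT parameters "between eyes with and without history of optic neuritis will be evaluated with a paired t-test or Wilcoxon signed-rank test". Section 6.6.3 foresees episodes during follow-up: "In case of acute optic neuritis or MS relapse the OCT assessment should be postponed for at least 30 days".

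SAP 2.5.2 and 2.7.2 state that no hypothesis is tested, and 2.7.2 calls the p-values descriptive.

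**The concern.** There are two worries.

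**The code.** LS means can be requested only for a fixed effect that is in the model. KRANK is not one, and the name appears nowhere else in the public text of either document. This is the only printed code for a listed secondary objective, and as it stands it does not produce the promised output. The protocol's paired t-test or signed-rank test would not produce LS means either.

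**The flag.** The outcome is change from baseline, and an eye could have its first optic neuritis after baseline. If such an eye were counted as having a history, eyes would be grouped by a post-baseline event that itself thins the nerve fibre layer (Protocol section 1 says that optic neuritis can do this). The difference between groups would then partly reflect how the groups were formed. No date is printed that excludes this.

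**Working it through.** No figure in the plan is at issue, so the check sets the statements side by side.

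**1. The code in SAP 5.3.2**

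| Statement | Effects named |
|---|---|
| CLASS | PATNO, OPT_NEUR |
| MODEL (fixed) | OPT_NEUR |
| RANDOM | PATNO |
| LSMEANS | KRANK |

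KRANK is in neither CLASS nor MODEL, so the LS-means request is invalid. A column called KRANK in the dataset would not rescue it, because it would still be absent from MODEL. The failure therefore cannot pass silently as a wrong table.

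Only one repair is possible. MODEL has a single fixed effect, OPT_NEUR, so that is the only effect for which LS means can be asked. SAP 2.5.4 independently names the same two groups and the same model.

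As a structural check, a random-intercept model was fitted in other software to invented data with 100 patients and 2 eyes each (100 × 2 = 200 eyes). With OPT_NEUR as the effect it returned a contrast and a p-value. With KRANK it stopped because the variable was undefined. The invented values say nothing about the trial, and SAS itself was not run.

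**2. How the SAP words the eye groups**

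| Place | Says *history*? | Dated? |
|---|---|---|
| 1.2, objective | yes | no |
| 1.2, endpoint cell | no | no |
| 2.5.4, first sentence | no | no |
| 2.5.4, second sentence | no | no |
| 5.3.2, lead-in to the code | no | no |
| 5.3.2, sentence defining the flag | yes | no |

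Two of six mentions say *history* and none is dated. The two that do are the ones that carry the definition: the objective and the flag sentence. The other four are short references to the same comparison. The protocol also says *history* in both its objective (3.2) and its analysis text (10.5.1).

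**3. What *history* means elsewhere in the protocol**

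- Section 7.2: the eye examination lists earlier eye history and new symptoms as separate items.
- Section 7.6.1: findings present before the trial go on the medical history form; significant later findings that meet the adverse-event definition go on the adverse event form.
- Section 6.6.3: on-study optic neuritis delays a scan; nothing there moves the eye to another group.

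All three point to history meaning before the study.

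**4. Does the exact cut-off matter (screening or V2)?**

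- Exclusion 12 bars acute optic neuritis in the 6 months before screening.
- Inclusion 6 bars relapse in the 30 days before V2.
- Screening runs from day -28 to day 0, that is 28 days, and 28 < 30.

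If acute optic neuritis counts as a relapse (an assumption), an eligible patient can have no episode between screening and V2. History before screening and history before V2 then give the same groups. The only eyes whose group depends on the reading are those with a first episode after V2, and *history* leaves them in the group without.

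**The case for a change.** The best case for a change is that an SAP should leave the programmer nothing to decide. Here the programmer must repair a line and, without a printed date, must choose the group of an eye with a first episode on study, perhaps after seeing the data. One word and one sentence would settle both.

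Some of this stands. The printed line is wrong, and a dated definition used consistently would read better. Neither is a reason to change the analysis. Correcting the name involves no choice. For the flag, following the text as worded gives the sound grouping; the harmful version requires reading *history* against its ordinary sense and against the protocol's own usage.

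The lack of a fallback in Protocol 10.5.1 carries no weight, since none is needed for a one-word repair. A paired test would in any case use only patients with one affected and one unaffected eye.

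Two possible additions, confidence limits for the difference and a count of eyes with on-study optic neuritis, go beyond what SAP 2.5.4 promises and are optional in a descriptive analysis. Onset dates for such a count would not be the obstacle: Protocol 8.1 requires start and end dates for adverse events, and 8.2 has relapses entered in the CRF. Only the affected eye is not shown to be recorded for on-study episodes.

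**Conclusion.** No change to the plan follows. The wrong name in SAP 5.3.2 is a clerical slip with a single possible repair. It would be found at the first run, and its numerical effect is nil: the model, eyes, grouping and outputs are already fixed by SAP 2.5.4 and by the rest of the code. The undated flag is missing detail that the wording itself fills, with history meaning before baseline. The documents do not allow the effect of the other reading to be sized or signed, and nothing in them shows a wrong result from following the plan. The primary analysis is untouched by either point.

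This rests on three things. The first is the general rule that LS means need a fixed effect in the model (SAS was not run). The second is the ordinary reading of *history*, supported by Protocol 7.2 and 7.6.1. The third, for the cut-off check only, is that acute optic neuritis counts as a relapse; patients who breach the entry criteria but stay in the full analysis set would be classified by date. Part of the SAP's definitions and its section 5.2 are not in the public text, so a dated definition may already exist there.
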